## 2 Rationale

### 2.1 Study rationale and purpose

There is growing evidence to support close interaction between the mTOR pathway and ER signaling. mTOR forms two different protein complexes, mTOR-raptor signal transduction complexes 1 and 2 (mTORC1 and mTORC2) (Guertin and Sabatini 2007). A substrate of mTORC1, p70 ribosomal S6 kinase (S9K1), directly phosphorylates the activation domain AF-1 of the ER, responsible for ligand-independent receptor activation (Yamnik et al 2009, Yamnik and Holz 2010). Preclinical studies suggest that sensitivity to hormonal therapy may be restored by treatment with everolimus or other mTOR inhibitors in breast cancer cells with upregulated Akt signaling (Baselga 2009). mTOR inhibitors given in combination with aromatase inhibitors (AIs) in preclinical models result in synergistic inhibition of proliferation and induction of apoptosis (Boulay et al 2005).

This extensive preclinical work suggests that co-targeting the mTOR pathway and ER signaling may improve the effectiveness of endocrine therapy. In addition, endocrine-resistant breast cancer cells demonstrate hyperactivation of the PI3K/mTOR pathway, and treatment with mTOR inhibitors including rapamycin analogs reverse this resistance (Miller et al 2010).

Results from recent clinical studies support these findings, as previously described in [Section 1.2.1.4](#). Combining everolimus with letrozole (Baselga et al 2009) in the neoadjuvant setting induced higher response rates than with letrozole alone in postmenopausal women with ER-positive breast cancer. The combination of everolimus with tamoxifen was also associated with prolonged PFS and improved overall survival (OS) in a phase II randomized study in patients progressing after prior AI treatment compared with tamoxifen alone (Bachelot et al 2012). An ongoing trial combining everolimus with fulvestrant in postmenopausal women with ER positive breast cancer has also shown encouraging activity (Badin et al 2010). In a recent pivotal phase III, randomized, double-blind, placebo-controlled trial, BOLERO-2, of everolimus plus exemestane versus exemestane plus placebo in ER positive postmenopausal women with locally advanced or metastatic disease refractory to letrozole or anastrozole, the addition of everolimus to exemestane prolonged median progression free survival 3.2 to 7.8 months based on local assessment (hazard ratio, 0.45; 95% confidence interval 0.38-0.54; p<0.0001) and 4.1 to 11 months based on central radiology review (hazard ratio, 0.38; 95% confidence interval 0.31-0.48; p<0.0001) (Baselga et al 2012, Yardley et al 2013).

Taken together, the above data support the activity of everolimus both in patients progressing after initial endocrine treatment and in patients who have not received prior treatment in the neoadjuvant setting. However, to date the efficacy of everolimus plus endocrine therapy has not been explored for first line therapy of patients with metastatic disease. Preclinical studies

have shown that inhibition of the PI3K/mTOR pathway can prevent the emergence of hormone-independent cells, suggesting that early intervention with combined endocrine therapy and mTOR inhibition may prevent or delay endocrine resistance ([Miller et al 2010](#)). It is also of interest to investigate whether continued mTOR inhibition with sequential endocrine therapy may provide clinical benefit. The proposed trial will assess the efficacy of everolimus plus letrozole in the first line treatment of patients with metastatic breast cancer and explore the efficacy of continued treatment with everolimus plus exemestane after initial progression.

## **2.2 Rationale for the study design**

This trial is designed to assess the progression free survival of patients treated with everolimus in combination with letrozole in the first line setting (primary study endpoint). It is also designed to evaluate the efficacy of continued therapy with everolimus in combination with a second endocrine agent, exemestane, in patients progressing on first line treatment (secondary study endpoint). Allowing patients to continue everolimus in combination with exemestane after progression will assess the effectiveness of continued treatment with everolimus in this patient population, who have progressed following first line treatment with everolimus plus letrozole. The study design will be open-label, single arm and will enroll a sufficient number of patients to allow a robust estimate of PFS in the first line setting.

### **2.2.1 Stomatitis therapeutic intervention**

Stomatitis, the inflammation of mucous membranes lining the mouth and throat, has been observed in approximately 44-64% of everolimus-treated patients (Afinitor PI). It is also a common adverse event associated with radiation and chemotherapy. Specific strategies to prevent and/or ameliorate the severity of everolimus-associated mucositis are not well documented. Caphosol is an oral mouth rinse indicated as an adjunct to standard oral care in the prevention and treatment of stomatitis caused by radiation or high dose chemotherapy. Low level laser therapy (LLLT) has also been suggested by the Multinational Association of Supportive Care in Cancer (MASCC) and the International Society for Oral Oncology (ISOO) to reduce the incidence of oral stomatitis and its associated pain in patients receiving high dose chemotherapy or chemo-radiotherapy ([Keefe et al 2007](#)). However, mTOR inhibitor-induced stomatitis is a different clinical entity, manifesting more frequently as discrete aphthous-like lesions rather than diffuse inflammation. A recent study evaluated the clinical presentation and management of stomatitis in 17 patients treated with an mTOR inhibitor. The majority of patients were treated with topical corticosteroids including an oral dexamethasone solution which was rinsed and expectorated. Clinical improvement was noted in over 85% of topical corticosteroid-treated patients ([de Oliveira et al 2011](#)). Additional reports from investigators indicate that an oral steroid rinse may help to ameliorate mTOR-induced stomatitis ([name], personal communication, February, 2012 and [name], personal communication, March 2012).

As a secondary endpoint, this trial will assess the effectiveness of treating stomatitis using an alcohol-free 0.5mg/5ml dexamethasone mouth rinse in countries where the solution is commercially available. At the onset of symptoms, enrolled patients will contact their physician. Based on preliminary confirmation of diagnosis, patients will be asked to visit the study site within 24 hours. Upon confirmation of the diagnosis of stomatitis the patient will be

randomly assigned to use either 0.5mg/5ml dexamethasone mouth rinse swished and expectorated 3 times per day or the standard of care normally used to treat stomatitis at the patient's center.

## 2.3 Rationale for dose and regimen selection

Letrozole has been selected for first line treatment in combination with everolimus and exemestane has been selected for second line treatment in combination with everolimus based on the following considerations:

- The activity of letrozole in the first line setting has been extensively documented ([Mouridsen et al 2003](#); [Park et al 2010](#), [Baselga et al 2009](#), [Krainich-Strobel et al 2008](#)).
- The combination of everolimus and letrozole has been investigated and is generally well tolerated ([Baselga et al 2009](#)).
- Exemestane in the second line setting has been established as an effective treatment in combination with everolimus in BOLERO-2 ([Baselga 2012](#), [Yardley 2013](#)).

Based on the current literature and product approvals, everolimus, letrozole and exemestane will all be given at the standard approved doses for first line and second line treatment in this patient population ([Baselga et al 2009](#), [Baselga et al 2012](#)).

## 2.4 Rationale for choice of combination drugs

The activity of letrozole in the first line setting has been extensively documented ([Mouridsen et al 2003](#); [Park et al 2010](#), [Baselga et al 2009](#), [Krainich-Strobel et al 2008](#)). Letrozole was chosen as the combination drug in the first line setting because of its approval in this setting and wide-spread use as first line endocrine therapy. Additionally, Baselga and colleagues combined everolimus 10mg daily and letrozole 2.5mg daily in the neoadjuvant setting and found that the combination induced higher response rates than letrozole alone in postmenopausal women with ER-positive breast cancer ([Baselga et al 2009](#)). The combination was well tolerated.

Exemestane in combination with everolimus has been established as an effective treatment in the second line setting. In phase III, randomized, double-blind, placebo-controlled trial, BOLERO-2, the combination of everolimus 10mg daily plus exemestane 25mg daily prolonged median progression free survival from 3.2 to 7.8 months based on local assessment (hazard ratio, 0.45; 95% confidence interval 0.38-0.54; p<0.0001) and 4.1 to 11 months based on central radiology review (hazard ratio, 0.38; 95% confidence interval 0.31-0.48; p<0.0001). The combination was generally well tolerated ([Yardley et al 2013](#)).

## 3 Objectives and endpoints

Objectives and related endpoints are described in [Table 3-1](#) below.

**Table 3-1 Objectives and related endpoints**

Objective	Endpoint	Analysis
Primary: The primary objective is to estimate progression-free survival in patients treated with everolimus + letrozole in the first line setting.	PFS	Refer to Section 10.4 .
Secondary: Determine the overall response rate and clinical benefit rate of everolimus + letrozole in the first line setting	ORR, CBR	Refer to Section 10.5.1 .
Determine the progression free survival, overall response rate and clinical benefit rate of everolimus + exemestane in second line population	PFS, ORR, CBR	Refer to Section 10.5.2 and Section 10.5.3 .
Evaluate the safety of everolimus + letrozole in the first line setting	Incidence of Adverse events	Refer to Section 10.5.5.2 .
Evaluate the safety of everolimus + exemestane in the second line setting	Incidence of Adverse events	Refer to Section 10.5.5.2 .
Estimate the overall survival of patients treated with everolimus + letrozole in the first line setting	OS	Refer to Section 10.5.4 .
Evaluate a therapeutic intervention to reduce the severity and duration of stomatitis	Oral Stomatitis Daily Questionnaire (OSDQ) data	Refer to Section 10.5.5.1 .
Evaluate clinical benefit as assessed by the Investigator during the Extension Phase	Proportion of patients with clinical benefit as assessed by the Investigator at scheduled visits	Refer to Section 10.5.5.3 .
Evaluate long term safety data	Frequency and severity of AEs/SAEs	Refer to Section 10.5.5.2 .

## 4 Study design

### 4.1 Description of study design

This is an open-label, phase II, multicenter, international, single-arm trial for patients with ER+, HER2- metastatic or locally advanced breast cancer. Enrolled patients will receive everolimus in combination with letrozole in the first line setting until disease progression or any other reason for which the patient may be discontinued (refer to [Section 7.1.5](#)). PFS in the first line setting is the primary study endpoint.

The study will be comprised of 2 phases:

- Core Phase: from FPFV to 24 months after LPFV and upon approval of amendment 5; safety and efficacy data (including PROs in selected subset) will be collected.
- Extension Phase: from the end of the Core Phase (upon approval of amendment 5) until LPLV of the Extension Phase for patients that are still deriving benefit at the end of the Core Phase. Patients may be transitioned to the Extension Phase and continue to receive the drugs up to 3 years or until progression or any other reason for which the patient may be discontinued (refer to [Section 7.1.5](#)); only safety and clinical benefit as assessed by investigator will be collected.

During the Core Phase following disease progression in the first line setting, patients will be offered everolimus in combination with exemestane. Patients who discontinue treatment in the first line setting due to unacceptable toxicity or due to withdrawal of consent will not be offered everolimus plus exemestane. Those patients treated in the second line setting will continue treatment until disease progression or any other reason for which the patient may be discontinued (refer to [Section 7.1.5](#)).

All patients who discontinue study treatment will have a 28 day follow up visit for safety and will be followed every 3 months thereafter for overall survival after completing treatment in either the first or second line treatment setting. Overall Survival will be followed until 24 months post LPFV.

At the first onset of symptoms suggestive of stomatitis patients will contact the study site. Upon confirmation of stomatitis, patients in countries where the alcohol-free 0.5mg/5ml dexamethasone oral solution is commercially available will be randomly assigned to take either 0.5mg/5ml dexamethasone mouth rinse or the standard of care used to treat stomatitis at the patient's center. The mouth rinse will be self-administered at a dose of 10ml 3 times per day. Patients will be instructed to swish and expectorate the mouth rinse. Patients will also be instructed to fill out the Oral Stomatitis Daily Questionnaire (OSDQ) at home every day until the patient recovers. For subsequent episodes of stomatitis patients will be instructed to contact the physician. Upon telephone confirmation, they will be instructed to utilize the same treatment they were assigned to after the first episode and complete the OSDQ booklet. **Note:** only those patients who develop symptoms suggestive of stomatitis and who have the diagnosis of stomatitis confirmed by the study site will participate in the investigation of the stomatitis intervention. OSDQ will not be administered during the Extension Phase.

[figure not shown]

The primary analysis of PFS for first line treatment will be performed 12 months after the last patient's recruitment. The analysis of PFS for second line treatment will be performed 6 months later (18 months after the last patient's recruitment) provided that the number of patients in second line treatment is adequate for a reliable PFS analysis. Otherwise, this analysis will be performed 24 months after the last patient's recruitment. The overall survival analysis will be performed 24 months after the last patient's recruitment. Assuming an enrollment period of 18 months, the expected trial duration is therefore 42 months.

Patients still benefiting from everolimus following the overall survival cutoff and following approval of Amendment 5 may continue treatment in the Extension Phase of the study. Patients may continue on their existing line treatment (1st or 2nd) in the extension up to 3 years or until the following: disease progression as deemed by physician judgement or any other reason for which the patient may be discontinued (refer to [Section 7.1.5](#)). Patients entering the Extension Phase on 1st line treatment and deemed to no longer be clinically benefiting will not be offered 2nd line treatment in the context of the study. Rather, these patients can start other standard treatments available or approved everolimus combination after exiting the study.

The extension will include required safety evaluations and standard of care, per investigator discretion and in consultation with the Sponsor.

**Figure 4-1** Study design

## 4.2 Early study termination

The study can be terminated at any time for any reason by Novartis. Should this be necessary, the patient should be seen as soon as possible and the same assessments should be performed as described in [Section 7](#) for a prematurely withdrawn patient. The investigator may be informed of additional procedures to be followed in order to ensure that adequate consideration is given to the protection of the patient's interests. The investigator will be responsible for informing IRBs and/or ECs of the early termination of the trial.

## 4.3 Definition of end of study

The planned overall study duration of the Core Phase will from FPFV until 24 months post LPFV and approval and implementation of Amendment 5. At the end of the Core Phase, if patients are still deriving benefit, patient may be transitioned to the Extension Phase which will last a total of 3 years (end of study). The LPLV is when the last patient has discontinued treatment for any reason in the Extension Phase and has had the 28 day safety follow up visit. The study closure will occur once the LPLV of the Extension Phase of the study has been documented.

# 5 Population

## 5.1 Patient population

Two hundred postmenopausal women with estrogen receptor positive HER2 negative metastatic or locally advanced breast cancer will be enrolled in this study. Patients enrolled in this study are not permitted to participate in additional parallel investigational drug or device studies.

The investigator or designee must ensure that only patients who meet all the following inclusion ([Section 5.2](#)) and none of the exclusion ([Section 5.3](#)) criteria are offered enrollment in the study. Upon enrollment patients will initiate first line treatment with everolimus plus letrozole.

All required screening evaluations must be performed to protect the safety of the patients and to ensure all inclusion and exclusion criteria are met. The results of all screening evaluations must be reviewed by the Principal Investigator or designee prior to enrollment of that patient onto the study.

All patients must be thoroughly informed about all aspects of the study including the study visit schedule, required evaluations and all regulatory requirements for informed consent. The written informed consent must be obtained before any screening evaluations are performed. If the patient is unable to read, an impartial witness should be present during the entire informed consent discussion.

Prior to patients being offered second line treatment with everolimus plus exemestane in the Core Phase, investigators must re-examine specified inclusion criteria 6, 7, 8, 9, 10 and exclusion criteria 8, 10, 12, 13, 14 as described in [Section 5.2](#) and [Section 5.3](#) below. Refer to [Section 7.1.3](#) for second line treatment procedures.

## 5.2 Inclusion criteria

Patients eligible for inclusion in this study have to meet all of the following criteria:

Written informed consent must be obtained prior to any screening procedures

1. Adult women (>18 years of age) with metastatic or locally advanced breast cancer not amenable to curative treatment by surgery or radiotherapy.
2. Histological or cytological confirmation of estrogen-receptor positive (ER+) human epidermal growth factor receptor 2 negative (HER2-) breast cancer.
3. Postmenopausal women. Postmenopausal status is defined either by:
  - a. Age  $\geq 55$  years and one year or more of amenorrhea
  - b. Age  $< 55$  years and one year or more of amenorrhea, with an estradiol assay  $< 20\text{pg/ml}$
  - c. Surgical menopause with bilateral oophorectomy
  - d. Note: Ovarian radiation or treatment with a luteinizing hormone-release hormone (LHRH) agonist (goserelin acetate or leuprolide acetate) is not permitted for induction of ovarian suppression.
4. No prior treatment for metastatic breast cancer
5. Patients must either have at least one lesion that can be accurately measured in at least one dimension  $>20\text{mm}$  with conventional imaging techniques or  $>10\text{mm}$  with spiral CT or MRI OR Bone lesions: lytic or mixed (lytic + sclerotic) in the absence of measurable disease as defined above
6. Adequate bone marrow and coagulation function as shown by:
  - a. Absolute neutrophil count (ANC)  $\geq 1.5 \times 10^9/\text{L}$
  - b. Platelets  $\geq 100 \times 10^9/\text{L}$
  - c. Hemoglobin (Hgb)  $> 9.0\text{g/dL}$
  - d. INR  $\leq 2$
7. Adequate liver function as shown by:
  - a. Serum aspartate aminotransferase (AST) and alanine aminotransferase (ALT)  $\leq 2.5 \times \text{ULN}$  (or  $\leq 5$  if hepatic metastases are present)
  - b. Total serum bilirubin  $< 1.5 \times \text{ULN}$  ( $< 3 \times \text{ULN}$  for patients known to have Gilberts Syndrome)
8. Adequate renal function as shown by:
  - a. Serum creatinine  $< 1.5 \times \text{ULN}$
9. Fasting serum cholesterol  $\leq 300\text{ mg/dL}$  or  $7.75\text{ mmol/L}$  and fasting triglycerides  $\leq 2.5 \times \text{ULN}$ .
10. ECOG Performance Status  $\leq 2$
11. Written informed consent obtained before any trial related activity and according to local guidelines.
12. Willingness to complete a daily stomatitis symptom questionnaire throughout each stomatitis event

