## Glossary of terms

Assessment	A procedure used to generate data required by the study
Cohort	A group of newly enrolled patients treated at a specific dose and regimen (i.e. treatment group) at the same time
Cycles	Number and timing or recommended repetitions of therapy are usually expressed as number of days (e.g.: q28 days)
Dose level	The dose of drug given to the patient (total daily or weekly etc.)
Enrollment	Point/time of patient entry into the study; the point at which informed consent must be obtained (i.e. prior to starting any of the procedures described in the protocol)
First line setting	Everolimus plus letrozole as first line treatment for patients with metastatic or locally advanced unresectable breast cancer
Second line setting	Everolimus plus exemestane treatment following progression on first line therapy with everolimus plus letrozole
Investigational drug	The study treatment whose properties are being tested in the study; this definition is consistent with US CFR 21 Section 312.3 and is synonymous with "investigational new drug."
Investigational treatment	Drug whose properties are being tested in the study as well as their associated placebo and active treatment controls (when applicable). This also includes approved drugs used outside of their indication/approved dosage, or that are tested in a fixed combination. Investigational treatment generally does not include other study treatments administered as concomitant background therapy required or allowed by the protocol when used in within approved indication/dosage
Medication number	A unique identifier on the label of each study treatment package which is linked to one of the treatment groups of a study
Other study treatment	Any drug administered to the patient as part of the required study procedures that was not included in the investigational treatment
Patient No.	A unique identifying number assigned to each patient/subject/healthy volunteer who enrolls in the study
Period	A subdivision of the study timeline; divides stages into smaller functional segments such as screening, baseline, titration, washout, etc.
Premature patient withdrawal	Point/time when the patient exits from the study prior to the planned completion of all study treatment administration and/or assessments; at this time all study treatment administration is discontinued and no further assessments are planned, unless the patient will be followed for progression and/or survival

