### 5.3 Exclusion criteria

Patients eligible for this study must not meet any of the following criteria:

1. Patients with only non-measurable lesions other than bone metastasis as defined above (e.g., pleural effusion, ascites, etc).
2. Patients who have received prior hormonal or any other systemic therapy for metastatic breast cancer.
  - a. Patients may have received prior neoadjuvant or adjuvant endocrine therapy. In the case of neoadjuvant or adjuvant NSAI (letrozole/anastrozole) therapy patients must have completed therapy at least 1 year prior to study enrollment.
3. Previous treatment with mTOR inhibitors.
4. Known hypersensitivity to mTOR inhibitors, e.g., sirolimus (rapamycin).
5. Another malignancy within 5 years prior to enrollment with the exception of adequately treated in-situ carcinoma of the cervix uteri, basal or squamous cell carcinoma or non-melanomatous skin cancer
6. Radiotherapy within four weeks prior to randomization except in case of localized radiotherapy for analgesic purpose of lytic lesions at risk of fracture which can then be completed within two weeks prior to enrollment.
7. Currently receiving hormone replacement therapy, unless discontinued prior to enrollment.
8. History of brain or other CNS metastases.
9. Patients receiving chronic treatment with systemic immunosuppressive agents
10. Bilateral diffuse lymphangitic carcinomatosis.
11. Patients with a known history of HIV seropositivity. Screening for HIV infection at baseline is not required.
12. Active bleeding diathesis.
13. Any severe and/or uncontrolled medical conditions such as:
  - a. Unstable angina pectoris, symptomatic congestive heart failure, myocardial infarction  $\leq$  6 months prior to enrollment, serious uncontrolled cardiac arrhythmia.
  - b. Uncontrolled diabetes as defined by fasting serum glucose  $>1.5 \times \text{ULN}$ .
  - c. Acute and chronic, active infectious disorders (except for Hep B and Hep C positive patients) and nonmalignant medical illness that are uncontrolled or whose control may be jeopardized by the complications of this study therapy
  - d. Impairment of gastrointestinal function or who have gastrointestinal disease that may significantly alter the absorption of study drugs (e.g., ulcerative disease, uncontrolled nausea, vomiting, diarrhea, malabsorption syndrome)
  - e. Active skin, mucosa, ocular or GI disorders of Grade  $>1$

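### The prior-treatment criteria name only metastatic disease, so read literally they admit women already treated systemically for unresectable locally advanced disease to a first-line estimate; inclusion 4 also conflicts with exclusions 2 and 6

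*Protocol*

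**What the plan says.** Section 5.2, inclusion 1, admits women with "metastatic or locally advanced breast cancer not amenable to curative treatment by surgery or radiotherapy". The Glossary defines the first line setting for the same two disease states: "Everolimus plus letrozole as first line treatment for patients with metastatic or locally advanced unresectable breast cancer".

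The criteria on prior treatment are narrower:

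- Inclusion 4 (Section 5.2): "No prior treatment for metastatic breast cancer".
- Exclusion 2 (Section 5.3): "Patients who have received prior hormonal or any other systemic therapy for metastatic breast cancer".
- Exclusion 2a: "Patients may have received prior neoadjuvant or adjuvant endocrine therapy". It adds an interval for one drug class: "In the case of neoadjuvant or adjuvant NSAI (letrozole/anastrozole) therapy patients must have completed therapy at least 1 year prior to study enrollment".
- Exclusion 3: "Previous treatment with mTOR inhibitors".
- Exclusion 6 bars recent radiotherapy but excepts "localized radiotherapy for analgesic purpose of lytic lesions at risk of fracture which can then be completed within two weeks prior to enrollment".

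The Protocol summary repeats inclusion 4 and exclusion 2 with the same limitation to metastatic disease. Section 10.1.1 puts every patient assigned first line treatment in the FAS, whatever her prior therapy. Section 10.4 makes first-line PFS in the FAS the primary estimate.

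**The concern.** Inclusion 4 and exclusion 2 are the criteria that make this a first-line trial, and they cover only one of the two disease states the trial enrols. A woman with unresectable locally advanced disease who had progressed on endocrine therapy or chemotherapy given for that disease would breach neither. The one-year NSAI interval does not catch her either, because it applies only to neoadjuvant or adjuvant use.

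The trial is single-arm. Section 10.8 sets the expected result beside roughly 9 months for an aromatase inhibitor alone as first line therapy. There is no control group to absorb a change in case mix, so if pretreated women are counted as first line, the median PFS, ORR and CBR describe a population other than the stated one.

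A second problem lies in the same sentence. Inclusion 4 bars treatment of any kind for metastatic disease, exclusion 2 bars systemic therapy only, and exclusion 6 allows a form of local treatment. Inclusion 5 deliberately admits patients with lytic bone disease and no measurable lesion, the group in which that local treatment is likely to occur.

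**Working it through.** **Eligibility, criterion by criterion.** Take a woman with unresectable locally advanced disease, without metastases, previously given systemic therapy with therapeutic intent for that disease.

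| Criterion | Does it exclude her? |
|---|---|
| Inclusion 1 | No; locally advanced disease is admitted |
| Inclusion 4 | No; it concerns metastatic disease |
| Exclusion 2 | No; it concerns metastatic disease |
| Exclusion 2a | No; it is a permission, and its NSAI interval covers neoadjuvant and adjuvant use only |
| Exclusion 3 | Only if she had an mTOR inhibitor |

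No other listed criterion addresses her earlier systemic therapy. She enters the FAS under Section 10.1.1.

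**Radiotherapy.** Take a woman with lytic bone metastases who has had localized analgesic radiotherapy to one of them. Exclusion 6 lets her in and exclusion 2 does not apply. Inclusion 4, read as written, keeps her out, because radiotherapy to a metastasis is treatment for metastatic disease. All inclusion criteria must be met, so the text gives two answers.

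**The plan's own precision figures.** Section 10.8 uses N = 200, 18 months of accrual, 12 months of further follow-up and 10% loss. With exponential PFS, uniform accrual and a dropout hazard of -ln(0.9)/30 per month, the expected events are 133.8 at a 12-month median and 123.1 at 14 months. The interval is median × exp(±1.96/√events):

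- 12 × exp(±1.96/√133.8) = 10.13 to 14.22
- 14 × exp(±1.96/√123.1) = 11.73 to 16.71

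Both match the table in Section 10.8. The eligibility gap changes no planning figure.

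**Illustration of a possible shift.** Let f be the share of pretreated women, m1 the median in untreated women and m2 the median in pretreated women, both exponential. The mixed median t solves (1-f)·2^(-t/m1) + f·2^(-t/m2) = 0.5. The Protocol does not give f, and m2 must be borrowed from other settings:

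- 7.8 months is the locally assessed median PFS with everolimus + exemestane in NSAI-refractory disease (Section 1.2.1.4).
- 17.4 months is the time to progression with everolimus + tamoxifen after an aromatase inhibitor, in the secondary-resistance subgroup (same section).

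| m1 | m2 | f = 5% | f = 10% | f = 20% |
|---|---|---|---|---|
| 12 | 7.8 | 11.73 | 11.47 | 10.97 |
| 12 | 17.4 | 12.21 | 12.43 | 12.88 |
| 14 | 7.8 | 13.58 | 13.17 | 12.38 |
| 14 | 17.4 | 14.15 | 14.30 | 14.60 |

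At f = 1% or 2% with m1 = 12 and m2 = 7.8, the median is 11.95 or 11.89, a shift of about 0.1 month or less. Every value for m1 = 12 lies inside 10.13 to 14.22, and every value for m1 = 14 inside 11.73 to 16.71.

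**The case against.** The best case on the other side is that this is a drafting omission and the intent is plain. The Glossary applies the first-line label to both disease states, and Section 5.1 says enrolled patients start first line treatment. Section 2.1 refers to metastatic disease alone where the matching sentence of the summary names both states, so the word may be shorthand. Exclusion 2a names the settings in which earlier endocrine therapy is acceptable, which invites the inference that other settings are not. This stands as evidence of intent. It does not close the gap: 2a is a permission attached to a bar on metastatic-disease therapy, and Section 5.1 tells investigators to apply the criteria in 5.2 and 5.3.

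There is also a safeguard. Section 7.1.1.1 requires the sponsor to confirm key eligibility criteria before enrollment, which may have screened such women out and reduced differences between sites. Its content is not shown, and it came with Amendment 3, which reports 56 patients enrolled as of 17 March 2014. It tempers the concern without correcting the text.

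On radiotherapy, the specific permission in exclusion 6 can be taken to override the general wording of inclusion 4. That is a sensible reading, but the Protocol does not state it.

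A reader might infer that the primary median is biased downward, by about a month at a 20% share. The documents do not support that. Shares of 5% to 20% mean 10 to 40 of 200 women, and nothing in the Protocol suggests such numbers. The 7.8 months comes from a different partner drug and a refractory population; the 17.4 months, equally borrowed and a different endpoint, reverses the sign. The trial tests no hypothesis, so no formal decision turns on the shift.

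**Conclusion.** The point holds as a defect in the eligibility text. Inclusion 4, exclusion 2 and their summary copies are narrower than the first-line population defined by inclusion 1 and the Glossary. Taken literally, they admit women already treated systemically for unresectable locally advanced disease to the FAS and to the primary estimate. Inclusion 4 also conflicts with exclusions 2 and 6 on which kinds of treatment count.

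The consequence for the result is not established. The Protocol does not show that any such woman was enrolled, gives no share, and does not fix the direction of a shift. The mixed medians rest on assumed shares, borrowed medians and exponential PFS. They show only that a small share has a small effect and that a large share could matter either way. The textual finding is firm; a claim of material bias would not be.

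**What to change.** Align inclusion 4, exclusion 2 and the Protocol summary to: no prior systemic therapy for metastatic or locally advanced unresectable breast cancer, other than neoadjuvant or adjuvant therapy as permitted in 2a. Limiting the bar to systemic therapy removes the clash with exclusion 6. The exemption is needed so that a woman given neoadjuvant endocrine therapy, whom 2a admits, is not newly excluded.

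The rewording changes no one's enrollment: the Amendment 5 rationale reports 202 patients enrolled, recruitment closed and the last patient's first visit on 17 December 2014. The operative step is analytic. Section 7.1.1.4 already collects each earlier anticancer therapy with its setting, including therapeutic. Count the patients with prior therapeutic-setting systemic therapy, state the number, and report first-line PFS, ORR and CBR with and without them as a sensitivity analysis. A count of zero would settle the matter. The primary analysis was due 12 months after the last recruitment, about December 2015, so an analysis added after it should be labelled post hoc.

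The cost is a few words in the criteria and one extra analysis on data already held.
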